In previous studies with Phased RFA an average acute procedural success of 98.2% (93-100%) was reported in patients with paroxysmal AF (23 studies). This is similar to the average acute procedural success reported for patients (6 studies) with persistent AF of 96.3%. In the case of index procedural failure, the authors linked the failure to the patient anatomy or characteristics and not to the Phased RFA system.

Endpoint definition:

- Procedure attempt was not declined due to technical issues related to Phased RFA system
- Only PVAC catheter(s) used to achieve PVI
AND
- All accessible PVs were isolated (entrance and/or exit block confirmation per vein)

If exit or entrance block was not verified during the procedure the data will not be used for this analysis.

Analysis Method: Acute procedural success rate will be reported as frequency and percentage at both the patients and vein level. Acute procedural success rate by patients will be calculated as number of patients with acute procedural success divided by number of patients with an attempted Phased RFA procedure. Acute procedural success rate by vein will be calculated as number of veins with electrical isolation verified divided by number of veins attempted with Phased RFA. 95% confidence intervals will be calculated using Fisher's exact method.

Limitation: Even though PVAC GOLD catheter has been designed anatomically, steerability can be influenced by the sheath used with the catheter. With fixed curve sheath might become challenging to reach all PVs, in particular right inferior PV due to technical issues. Due to this additional use of 3D system and irrigated catheters might be utilized by the medical centers where steerable sheath is not available.

Assess Phased RFA efficiency

Rational: The multi electrode catheter technology delivers continuous lesions and shortens procedure times. The ability to map and ablate with the same electrode simplifies and shortens the procedure.

Procedure duration is impacted by the maneuverability of the catheter. The new catheter design of the PVAC GOLD array allows enhanced tissue contact due to the 20° forward tilt.

Hospital resource allocation is another indicator of procedural efficiency, reflected by the procedure duration ("from skin to skin"), laboratory occupancy ("from door to door"), fluoroscopy time as well as number of used catheters and adjunctive devices (mapping and navigation) used.

Endpoint definition:

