### 8.3.1 Characterize the acute procedural success rate

Success rates will be calculated for all documented procedures combined (patient level). Also, procedure success rates will be provided for first documented procedures, additional procedures, regular cases and training cases, separately. Success rates will also be shown per vein.

Success will be calculated for procedures that have been attempted (number of RF applications per patient > 0). Success rates will be provided for PVAC GOLD solely procedures (ancillary objective) and additionally for not PVAC GOLD solely procedures (using other catheter and/or using adjunctive devices).

If RF applications per patient, consumables (Phased RFA catheters used), successfulness and PV confirmation (exit or entrance block) was not verified for the procedure, the data will not be used for analysis. Consumables and procedure success will be taken from the procedure form. Relatedness of Phased RFA will be taken from AE form.

The procedure is considered successful if:

- Procedure attempt was not declined due to technical issues related to Phased RFA system and
- Only PVAC catheter(s) used to achieve PVI and
- All accessible PVs were isolated (entrance and/or exit block confirmation per vein)

This combined endpoint (variables linked via “and operation”) is applicable, if all conditions are available and complied.

Because of different procedure forms (eCRF V1.3 and eCRF V1.4), PVI achievement by PVAC GOLD only is assumed for patients documented by eCRF V1.3 as follows:

- [F21000010] Phased RFA catheter used: only PVAC GOLD is ticked, and
- [F22000010] to [F22000060] PVI confirmation: exit block and/or entrance block are ticked, and
- [F20001000] Number of RF applications per patient > 0

Unsuccessfulness per vein is considered, if the vein is not isolated or not verified. Percentages for success will be shown per vein for patients treated with PVAC GOLD solely. Precondition is that the number of RF applications per patient is greater than zero.

PVI achievement by PVAC GOLD only is defined for patients documented by eCRF V1.4 as follows:

- [F21000010] Phased RFA catheter used: only PVAC GOLD is ticked, and
- [F22000062] Where all PVs isolated at the end of the procedure = yes, and
- [F22000066] Where all PVs isolated by using PVAC only = yes, and
- [F21000010] Number of RF applications per patient > 0

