### 8.3.1.1 Methodology for analysing the acute procedural success rate

Acute procedural success rate will be reported as frequency and percentages. Acute procedural success rate by patients will be calculated as number of patients with acute procedural success divided by number of patients with an attempted Phased RFA procedure. Acute procedural success rate by vein will be calculated as number of veins with electrical isolation verified divided by number of veins attempted with Phased RFA. 95% confidence intervals will be calculated using Fisher's exact method.

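### SAP 8.3.1 labels acute success among sole-PVAC-GOLD procedures as the ancillary objective, while SAP 8.3.1.1 and Protocol 4.4.3 divide by all attempted patients; its eCRF V1.4 rule also misapplies one success condition

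*SAP*

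**What the plan says.** Protocol 4.4.3 and SAP 8.3.1 define acute success by the same three conditions, all required: the attempt was not abandoned for technical reasons tied to the system; "Only PVAC catheter(s) used to achieve PVI"; and every reachable vein was isolated, with block confirmed.

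The denominator is described in three places.

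- **Protocol 4.4.3 and SAP 8.3.1.1** give the same patient-level formula: "number of patients with acute procedural success divided by number of patients with an attempted Phased RFA procedure".
- **SAP 8.3.1, opening**, plans an overall rate: "Success rates will be calculated for all documented procedures combined (patient level"). It defines an attempt without reference to the catheter: "Success will be calculated for procedures that have been attempted (number of RF applications per patient > 0").
- **SAP 8.3.1, next sentence**, attaches the objective to a subset: "Success rates will be provided for PVAC GOLD solely procedures (ancillary objective) and additionally for not PVAC GOLD solely procedures". The bracket that follows describes the second group as procedures in which another catheter, an adjunctive device, or both were used.

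SAP 8.3.4 and the matching subgroup in SAP Appendix C also exclude adjunctive devices from sole PVAC GOLD use. Appendix C further requires that one catheter was used.

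For data handling, SAP 8.3.1 says that PVAC-only isolation is assumed for patients on eCRF V1.3 and defined for those on V1.4. Both rules require that PVAC GOLD is the only entry in F21000010, which lists the Phased RFA catheters used. V1.4 adds two direct questions: were all veins isolated at the end (F22000062), and were they all isolated with PVAC only (F22000066).

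**The concern.** The condition that separates the two strata overlaps with a condition for success. In the stratum that carries the objective's label, isolation with PVAC alone is largely met by selection. The labelled rate then says little about how often PVAC GOLD needed help, which is a main way for this endpoint to fail. The protocol foresees such help: "additional use of 3D system and irrigated catheters might be utilized by the medical centers where steerable sheath is not available".

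The SAP therefore holds two rates for one named objective and does not say which is the result. Protocol 4.4 expects changes to its analysis methods to be described and justified in the SAP. The SAP announces departures elsewhere (7.2.3 on visit windows, 8.1.1 on the recurrence definition), but gives no such notice here.

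A second problem runs in the opposite direction. The condition is worded as "Only PVAC catheter(s) used to achieve PVI and", so it concerns catheters used to isolate the veins. F21000010 covers every Phased RFA catheter used in the procedure, including MAAC and MASC. Protocol 3.3 describes those two as designed for lesions in other regions of the left atrium, especially in persistent AF.

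**Working it through.** The documents state no target, sample size or expected rescue rate for acute success, so there is no planned figure to reproduce. The size is shown by illustration.

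**1. The two denominators**

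Inputs, all assumed, per 1,000 attempted patients with usable data:

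- t = patients who needed another catheter to complete PVI: 20, 50 or 100
- u = patients not isolated and treated with PVAC GOLD alone: 20
- nobody is outside the sole-use stratum for any other reason

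Formulas:

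- All attempted (Protocol 4.4.3, SAP 8.3.1.1): (1000 − t − u) / 1000
- Sole-use stratum (labelled in SAP 8.3.1): (1000 − t − u) / (1000 − t)

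| t | All attempted | Sole-use stratum | Gap (points) |
|---|---|---|---|
| 20 (2%) | 960/1000 = 96.0% | 960/980 = 98.0% | 2.0 |
| 50 (5%) | 930/1000 = 93.0% | 930/950 = 97.9% | 4.9 |
| 100 (10%) | 880/1000 = 88.0% | 880/900 = 97.8% | 9.8 |

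In general the gap is s × q, where s is success within the stratum and q is the share rescued. The stratum rate hardly moves as q rises from 2% to 10%, while the all-attempted rate falls by 8 points.

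To compare the gap with sampling error, take s = 98.2%, the protocol's literature average for paroxysmal AF, and q = 5%. The exact (Clopper-Pearson) 95% intervals are:

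- sole-use stratum, 933/950 = 98.2%: 97.2 to 99.0
- all attempted, 933/1000 = 93.3%: 91.6 to 94.8

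The two rates share the same successes, so this is not a test. It shows only that the choice of denominator can outweigh the imprecision.

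**2. The V1.4 field rule**

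Take a patient with persistent AF whose veins were all isolated with PVAC GOLD and who then had MAAC lesions elsewhere in the left atrium.

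| Item | Value | Needed by the V1.4 rule |
|---|---|---|
| F22000062, all veins isolated | yes | yes |
| F22000066, isolated with PVAC only | yes | yes |
| RF applications | > 0 | > 0 |
| F21000010, Phased RFA catheters | PVAC GOLD and MAAC | PVAC GOLD only |

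As worded, the condition is met, because no other catheter was used to isolate a vein. Under the field rule it is not met. Each 1% of attempted patients in this position who would otherwise be successes takes 1 percentage point off the all-attempted rate. The documents give no figure for that share.

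**The case against.** **Rescued patients do count somewhere.** A reader might infer that patients who needed another catheter can never be failures under this SAP. The documents do not support that. SAP 8.3.1 plans a combined patient-level rate, attempts are defined without a catheter condition, and SAP 8.3.1.1 keeps these patients in the denominator, where they fail. SAP 8.3.1 also reports the other stratum and, for V1.4, plans per-vein percentages where PVAC alone did not isolate all veins. This stands. What remains is that the objective's label sits on the subset.

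**Sole use could be read differently.** If it were taken from F21000010 alone, a V1.4 patient finished with an irrigated catheter could stay in the stratum and fail through F22000066. The SAP does not rule this out. The bracket in 8.3.1, section 8.3.4 and Appendix C all favour the reading that excludes other catheters or adjunctive devices.

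**The other stratum is not bound to be zero.** A patient isolated with PVAC alone under a mapping system can still succeed there. Only those who needed another catheter for PVI must fail.

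**V1.3 touch-ups.** It is tempting to say that V1.3 patients finished with a non-Phased catheter pass as PVAC-only successes, because the V1.3 rule ignores F21000040 and F21000050. SAP Table 10 labels those fields as mapping or navigation systems. Whether they, or the free text in F21000020, record ablation catheters depends on the annotated eCRF, which is not in the text reviewed. The SAP also says openly that V1.3 rests on an assumption. The point is therefore conditional.

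**Benchmarks.** The 98.2% and 96.3% in Protocol 4.4.3 are background. Neither document says that the registry's rate will be compared with them. The analysis is descriptive.

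**Conclusion.** The inconsistency is real and limited to an ancillary, descriptive objective. SAP 8.3.1 labels a rate conditioned on something close to its own success condition, while SAP 8.3.1.1 and Protocol 4.4.3 set the denominator as all attempted patients. If sole use excludes other catheters and adjunctive devices, the labelled rate would exceed the all-attempted rate by about 2, 5 or 10 points at assumed rescue rates of 2%, 5% or 10%. These figures assume that every rescued patient fails the PVAC-only condition and that 2% of attempted patients are not isolated.

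The V1.4 rule is a separate misclassification. It scores PVAC-only isolation followed by MAAC or MASC work as a failure of a condition that, as worded, was met. This would fall mainly on persistent AF, and its size cannot be given from the documents. The main objective's endpoint definition is not affected by either problem.

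**What to change.** 1. In SAP 8.3.1, name the all-attempted patient-level rate of 8.3.1.1 as the result for the ancillary objective. State that a patient who needed a non-PVAC catheter to achieve PVI stays in the denominator as a failure.
2. Keep the split by sole or non-sole PVAC GOLD use as a labelled descriptive table, and say which fields define sole use.
3. For eCRF V1.4, take the PVAC-only condition from F22000062 and F22000066, and drop the requirement that only PVAC GOLD is ticked in F21000010.
4. For eCRF V1.3, look at the annotated form. If the adjunctive-device and free-text fields record non-Phased ablation catheters, add a check on them. If they do not, report V1.3 and V1.4 rates separately.

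The V1.4 change needs only SAP wording and programming on fields the SAP already lists. The V1.3 check depends on what the form holds. The reported rate may be a few points lower than the sole-use figure, partly offset where step 3 restores patients who had MAAC or MASC work after PVAC-only isolation.

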- Total lab occupancy time is defined as time patients enters the EP room to time patients' is out of EP room.
- Total procedure time is defined as time of first venous access to time of last catheter removal.
- Total fluoroscopy time is defined as time of elapsed fluoroscopy time at time of first catheter insertion to elapsed fluoroscopy time at time of last ablation catheter removal.
- Left atrium dwell time is defined as time from first Phased RFA catheter insertion to last Phased RFA catheter removal.
- Total Phased RFA time is defined as the sum of durations in which Phased RFA catheter is applied to pulmonary veins.
- Adjunctive devices: additional use of non-Phased RFA catheters, mapping or navigation systems to achieve PVI
- Adjunctive devices (mapping or navigation systems)

Measurement: Will be taken during the Phased RFA procedure.

Analysis Methods: Procedure parameters including procedure times, number of applications, duration will be summarized using n, mean, SD, minimum, median, or IQR, minimum and maximum. Parameters may be presented as summaries by patients and by pulmonary vein.

Limitations: no limitations are known for these parameters.

Characterize the peri -procedural anticoagulation therapy

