### 4.2 Baseline Analysis Set

The *Baseline Analysis Set* (BAS) consists of all patients of the APS and patients:

- where baseline signature has been taken (signed eCRF)
- with AF who are scheduled for Phased RFA
- that meet all remaining eligibility criteria
- provide any further documentation at baseline
- a phased RFA procedure was started - procedure form was fulfilled at least: date of the procedure, PVAC GOLD catheter used (opened), number of PV applications > 0
- patient did not exit the study prematurely for the reason: Patient were enrolled, but Phased RFA procedure was not started

According to the Appendix B, the BAS will be used for the interim and final analysis as well as for post-hoc analysis. The final analysis includes the additional objective (SAP chapter 8.2) and ancillary objectives (SAP chapter 8.3), where the BAS will be applied.

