## Appendix C: Subgroup analysis

Predefined subgroups (V1.0)

Subgroup description	Analysis set, additional inclusion or exclusion criteria	Tables and scope for analysis
Indication to schedule Phased RFA: Paroxysmal AF	FAS, EFAS incl.: --- excl.: ---	Baseline First documented procedure Additional procedure 12MFU
Indication to schedule Phased RFA: Persistent AF	FAS, EFAS incl.: --- excl.: ---	Baseline First documented procedure Additional procedure 12MFU
Indication to schedule Phased RFA: Longstanding persistent AF	FAS, EFAS incl.: --- excl.: ---	Baseline First documented procedure Additional procedure 12MFU
Successful first documented procedure	FAS, EFAS incl.: --- excl.: ---	Baseline First documented procedure Additional procedure 12MFU
Non-successful first documented procedure	FAS, EFAS incl.: --- excl.: ---	Baseline First documented procedure Additional procedure 12MFU
First documented procedure: PVAC GOLD solely	FAS, EFAS incl.: Phased RFA catheters = PVAC GOLD, general number if catheters used = 1 excl.: adjunctive devices used during the procedure, disregarding sheaths used	First documented procedure Additional procedure GFU 12MFU
First documented procedure: PVAC GOLD + other catheters	FAS, EFAS incl.: Phased RFA catheters = PVAC GOLD, general number if catheters used > 1, additional Phased catheter used (MAAC, MASC and/or Other) excl.: adjunctive devices used during the procedure, disregarding sheaths used	First documented procedure Additional procedure GFU 12MFU
First documented procedure: Phased RFA catheter solely	FAS, EFAS incl.: Phased RFA catheters used, general number if catheters used = 1 excl.: adjunctive devices used during the procedure, disregarding sheaths used	First documented procedure Additional procedure GFU 12MFU
First documented procedure: Phased RFA catheter + adjunctive devices	FAS, EFAS incl.: Phased RFA catheters = PVAC GOLD, general number if catheters used > 1, additional Phased catheter used (MAAC, MASC and/or Other), adjunctive devices used during the procedure excl.: ---	First documented procedure Additional procedure GFU 12MFU
Procedure: Patients with multiple procedures	FAS, EFAS	Baseline First documented procedure Additional procedure

	incl.: patients with > 1 documented procedure excl.: ---	GFU 12MFU

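### The eCRF V1.3 rule for isolation by PVAC GOLD only can miss a non-Phased catheter, and the Appendix C adjunctive-device group omits PVAC GOLD used alone with an adjunct

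*SAP*

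**What the plan says.** **Acute success.** Protocol 4.4.3 and SAP 8.3.1 share the endpoint: no failure from technical issues with the system, only PVAC catheters used to achieve PVI, and all accessible veins isolated.

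- *eCRF V1.3.* The SAP states "PVI achievement by PVAC GOLD only is assumed for patients documented by eCRF V1.3 as follows". The three conditions are PVAC GOLD as the only tick in the Phased RFA catheter field (F21000010), "PVI confirmation: exit block and/or entrance block are ticked, and" more than zero RF applications.
- *eCRF V1.4.* The rule also requires a yes to F22000066, which asks whether all veins were isolated using PVAC only. SAP Table 9 marks this item as V1.4 only.
- *Strata.* SAP 8.3.1 also reports success for "not PVAC GOLD solely procedures (using other catheter and/or using adjunctive devices"). It plans no split by eCRF version.

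**Adjunctive devices.** Protocol 4.4.3, under Phased RFA efficiency, lists "Adjunctive devices: additional use of non-Phased RFA catheters, mapping or navigation systems to achieve PVI". A second bullet there, and SAP Table 10, describe adjunctive devices only as mapping or navigation systems. The acute-success limitation in Protocol 4.4.3 expects irrigated catheters and 3D systems at some centres.

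**Appendix C** defines four groups by catheter and device at the first documented procedure:

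- G1, *PVAC GOLD solely*: PVAC GOLD, one catheter, adjunctive devices excluded.
- G2, *PVAC GOLD + other catheters*: more than one catheter, an additional Phased catheter, adjunctive devices excluded.
- G3, *Phased RFA catheter solely*: "incl.: Phased RFA catheters used, general number if catheters used = 1", adjunctive devices excluded.
- G4, *Phased RFA catheter + adjunctive devices*: PVAC GOLD, more than one catheter, "additional Phased catheter used (MAAC, MASC and/or Other), adjunctive devices used during the procedure".

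All four use the FAS and EFAS, which are subsets of the BAS. BAS entry requires "PVAC GOLD catheter used (opened), number of PV applications > 0".

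**The concern.** The V1.3 conditions show which Phased catheter was used and that the veins were isolated. They do not show which device isolated them. The fields where a non-Phased catheter might appear are the catheter count (F21000005), the free text (F21000020) and the adjunctive-device fields (F21000040 and F21000050). SAP Table 10 lists all of them for both eCRF versions, but the V1.3 rule uses none of them. The pooled success rate can therefore combine two definitions, and any error runs towards success.

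In Appendix C the criteria for G4 do not match its title. Patients in G4 differ from those in G1 in two ways at once: an adjunct and an extra Phased catheter. G4 feeds 12-month tables, and SAP 8.1.2 plans Cox models for predefined subgroups with a 12-month scope. A result for G4 cannot be attributed to adjunct use.

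**Working it through.** The plan states no figure on this point to reproduce, so the check applies the rules as written to every combination of catheters and devices.

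**Set-up.** PVAC GOLD is always present (BAS criterion). Three items vary: another Phased catheter, a non-Phased ablation catheter, and an entry in the adjunctive-device fields. Comma lists in G1 to G4 are read as *and*. The annotated eCRF (SAP Appendix E) is not in the reviewed text, so two questions stay open and both answers are run:

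- Does the catheter count include non-Phased catheters?
- Can the *Other* tick among the Phased catheters record a non-Phased one?

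The four readings are A (no, no), B (no, yes), C (yes, no) and D (yes, yes).

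| Used with PVAC GOLD | Passes V1.3 rule | Appendix C group |
|---|---|---|
| Nothing else | A, B, C, D | G1 and G3 in all |
| Adjunct only | A, B, C, D | None in all |
| Non-Phased catheter, no adjunct entry | A, C | A: G1 and G3; B: G3; C: none; D: G2 |
| Non-Phased catheter and adjunct entry | A, C | A, B, C: none; D: G4 |
| Other Phased catheter, no adjunct | None | G2 in all |
| Other Phased catheter and adjunct | None | G4 in all |

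Adding a non-Phased catheter to the last two rows changes nothing.

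**Results.**

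1. The V1.3 rule rejects another Phased catheter in all four readings.
2. It passes PVI completed with a non-Phased catheter in two of four readings, those where the *Other* tick cannot record one. On V1.4 the same procedure fails at F22000066.
3. PVAC GOLD as sole catheter plus an adjunct is in no Appendix C group in all four readings.
4. G1 and G3 hold the same patients in three of four readings. The exception is B, where a catheter is ticked as *Other* yet left out of the count. The identity follows from the BAS criterion; without it the groups would differ.

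**Scale (assumptions, not estimates).** Let *s* be the share of procedures on V1.3 and *t* the share of those isolated with a non-Phased catheter that the rule misses. The pooled rate is overstated by at most *s* × *t*, in percentage points:

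| *s* | *t* = 1% | 5% | 10% | 15% |
|---|---|---|---|---|
| 0.25 | 0.25 | 1.25 | 2.5 | 3.75 |
| 0.50 | 0.5 | 2.5 | 5.0 | 7.5 |
| 0.75 | 0.75 | 3.75 | 7.5 | 11.25 |

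For comparison, Protocol section 1 cites an average acute success of 98%. By the normal approximation without a design effect, the 95% half-width is 1.96 × √(0.98 × 0.02 / *n*): 0.97 points at *n* = 800 and 0.87 at *n* = 1000. With *s* = 0.5, *t* = 2% gives 1 point, about the same size.

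Neither *s* nor *t* is in the documents. The form dates (30-Apr-2015 and 13-Jan-2017) are 20.5 months apart. Set against recruitment from Q1 2015 to Q2 2018 (42 months), that is 20.5 / 42 = 49%. Turning this into a patient share would require even enrolment and form dates equal to deployment dates.

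**The case against.** The strongest reply has five parts.

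- **The rule does check catheters.** Any tick other than PVAC GOLD fails it. A reader might infer that it never looks for other ablation catheters; that is wrong, because other Phased catheters are caught. If sites enter irrigated catheters under *Other*, the rule catches those too. This stands, and it is why the bias is possible rather than shown.
- **An adjunct does not in itself contradict the endpoint.** A mapping system isolates no vein. SAP Table 10 describes adjunctive devices as mapping or navigation only, so the adjunctive fields may not record irrigated catheters. This stands. It limits what the added check may find, and makes reporting by eCRF version the more secure safeguard.
- **The plan is open about the difference.** SAP 8.3.1 calls the V1.3 attribution an assumption and explains that the forms differ. That is true, but without results by version a reader of the report could not see its effect.
- **The comparison with adjuncts exists elsewhere.** One might infer from Appendix C that it is lost. It is not: SAP 8.3.1 for acute success and 8.3.2 for times report *solely* and other procedures separately. Neither section covers 12-month outcomes, where the G4 problem remains.
- **Appendix C is descriptive and need not be exhaustive, and its commas do not always mean *and*.** The group for prior AF surgery or ablation lists alternatives. Both points are fair. But reading every comma in G4 as *or* would admit every patient, since all had PVAC GOLD. Reading only the last comma as *or* still leaves the requirement of more than one catheter, so sole PVAC GOLD plus an adjunct stays out unless the adjunct itself counts as a catheter.

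**Conclusion.** The point holds in limited form, and it is minor.

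- **V1.3 rule.** Isolation completed with a non-Phased catheter can count as a PVAC-only success on V1.3 and not on V1.4. The pooled acute success rate can mix two definitions and can be biased upward. The documents do not support saying that it is inflated, or by how much: the frequency of such procedures and the V1.3 share are not given, and whether *Other* catches them depends on the eCRF.
- **G4.** Its criteria do not fit its title. PVAC GOLD as sole catheter plus an adjunct is in none of the four groups, and the group's 12-month results confound adjunct use with extra Phased catheters. It is tempting to say that half the possible combinations are ungrouped. Only this one is ungrouped under every reading; the rest depend on how catheters are counted and ticked.
- **G3.** It in effect duplicates G1. This is redundant but does no harm.

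The main objective is unaffected, apart from the descriptive subgroup results and Cox models that use the Appendix C groups.

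**What to change.** 1. **SAP 8.3.1, V1.3 rule.** Also require that F21000005, F21000020 and F21000040/F21000050 show no non-Phased ablation catheter. State that mapping or navigation alone does not disqualify.
2. **Reporting.** Give acute success by eCRF version as well as pooled.
3. **Unresolved V1.3 cases.** Apply the existing SAP 8.3.1 rule that unverified data are not used, which agrees with the observed-cases rule in SAP 7.5.1. Add a sensitivity analysis counting these cases as not PVAC-only. Making that the main rule would turn unknowns into failures and replace a possible upward bias with a downward one.
4. **SAP Appendix C.** Define the adjunctive group as any Phased RFA catheter plus an adjunctive device, whatever the catheter number. Split it by whether an additional Phased catheter was used. Merge G3 with G1 or delete it.

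The cost is SAP wording and a little programming, with some free-text review, on fields already collected. The reported acute success rate may turn out slightly lower.
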